9.2 Imaging Analyses

At the end of the study, all images will be evaluated by central review. Please see Appendix H for details. All imaging from initial diagnosis and/or prior to radiotherapy, as well as available imaging collected on study and/or in follow up must be submitted for central review and study analyses. Examples of imaging analyses may include, but are not limited to, descriptive correlation of imaging characteristics and clinical outcomes, and imaging correlates with treatment response or resistance.

10. STATISTICAL CONSIDERATIONS

10.1 Study Design/Endpoints

This is an open-label, prospective, multi institutional safety and early efficacy protocol. All subjects will be treated at a PNOG Institution or participating institution for this study. The primary endpoint is safety; the secondary endpoint is a preliminary estimate of efficacy.

Primary Endpoint:

- Safety and toxicity measurements of repeated CED administration of MTX110 following standard of care focal radiotherapy using CTCAE version 4.0 in newly diagnosed subjects with DIPG.

Secondary Endpoint:

- OS at 12 months (OS12) in newly diagnosed subjects with DIPG.

[figure not shown]
Exploratory Endpoints:

- Assessment of observed distribution of gadoteridol compared to pre-treatment modeling of the drug distribution utilizing predictive imaging software.
- The Quality of Life exploratory endpoint associated with this study will be descriptive and will be limited to frequency tables and summary statistics.
- To perform central review of imaging to explore MR qualitative and quantitative measures as markers of disease response and/or progression and treatment effect in comparison to institutional evaluation of disease response and/or progression.

10.2 Dose Escalation

Initially an accelerated titration design (ATD; diagram 1) will be employed. This design has the advantage of potentially reducing the number of subjects treated at sub-eficacious doses, and decreasing the accrual time for the trial. Each cohort will consist of one subject. The first subject will be started at dose level 1. A 14-day window of evaluation for toxicities is required for at least one subject at each dose level before determining the dose for the next cohort.

Diagram 1. Accelerated trial design.

[figure not shown]
Intra-patient dose modification (Diagram 2) will be allowed as follows: dose escalation (following the dose levels in Table 5.2.1) is permitted if a subject experiences a toxicity of grade 0 or 1; dose de-escalation will be followed if the toxicity is dose limiting toxicity (DLT) or worse (i.e., an intolerable grade 2 or grade 3 and above, as defined in Section 5.3); while the dose will remain unchanged if a subject experiences a moderate toxicity (i.e., moderate grade 2). At the second occurrence of any grade 2 toxicity during the first treatment cycle, or the first DLT occurrence during the first treatment cycle, the ATD will be transitioned to a standard 3+3 dose escalation design. That is, two additional subjects will be accrued at the dose level that triggered the transition. As in a standard 3+3 dose escalation design, there are three possible scenarios for this cohort of 3 subjects, if there are (is):

- two or three DLTs, the RP2D will be defined as the next lower dose level;
- zero DLTs (i.e., the transition from the ATD to the 3+3 design was triggered by the second occurrence of a grade 2 toxicity as opposed to a DLT and no DLTs were observed in the additional 2 subjects), the dose escalation will occur based on Table 5.2.1;
- one DLT, an additional 3 subjects will be entered at the same dose level.

In the last scenario with six subjects at the current dose there are two subsequent scenarios:

- only one DLT and then dose escalation can occur based on Table 5.2.1.
- more than one DLT and then the next lower dose level is the RP2D.

Diagram 2. Intra-patient dose escalation.

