¹ from October 2016

Summary of adverse events with cut off date Oct 31, 2018 of the current study.

To date, we have enrolled █ subjects and completed monitoring and DSMC approval of the first 4 dose levels as per the ATD. There were no DLTs at any dose level. Table 13 details related adverse events reported to date.

Table 13. Adverse events probably, possibly or definitely related to protocol therapy:

			Maximum grade across all cycles			
			Grade 1	Grade 2	Grade 3	Grade 4
Toxicity	Dose level	# Evaluable Patients				
Fatigue	4	1	1	-	-	-

Summary of preclinical and clinical data

In summary, the relevant preclinical and clinical studies support the exploration of CED of MTX110 in children with DIPG:

- (1) The target of MTX110 is highly expressed in human DIPGs
- (2) Human derived DIPG cell lines are sensitive to MTX110
- (3) CED leads to effective distribution within the brainstem
- (4) CED of MTX110 under real time imaging is feasible
- (5) Published evidence supports the feasibility of CED in children with DIPG
- (6) Five total pediatric patients with DIPG receiving MTX110 via CED support safety of delivery of MTX110 via the proposed CED protocol.

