10.3 Sample Size and Accrual

The number of subjects enrolled in the safety study will depend upon the DLTs observed and the number of dose levels tested as the study progresses in accordance with an ATD followed by a 3+3 design. The ATD is expected to enroll 1 to 7 subjects with a minimum of 5 subjects in the 3+3 design. Additional subjects may be enrolled depending on the dose de-escalations, expansion of dose exploration, or exploration of intermediate doses that occur. Once these dose levels have been assessed, a detailed review of the safety and efficacy data will be performed and discussed with the FDA and the DSMC to discuss either further dose escalation or enrollment into the efficacy study.

Secondary Objective: The most recent Children’s Oncology Group study that treated children newly diagnosed with DIPG with a combination of radiation therapy and temozolomide resulted in an OS12 rate of 40% (SD ± 6.5%). A sample size of 19 patients achieves 80% power to detect a difference of 30% using a one sided exact binominal test. The target significance level is 5% and the actual significance level is 3.5% with this test. If 12 or more patients are alive at 12 months, the null hypothesis that OS12 is 40% will be rejected.

Stopping Rules:

Both the ATD and 3+3 have inherent stopping rules; however, it should be noted that this study will be stopped for further review by the DSMC and study team as well as FDA by:

- The occurrence of 1 or more irreversible neurological deficits that are grade 3 or higher and definitely related to the procedure based on evidence on MRI such as intraparenchymal hemorrhage, worsening edema or necrosis.

- If more than 20% of subjects develop significant, irreversible deterioration during the infusion.
- If more than 20% of subjects do not get study drug infused due to surgical complications during the catheter placement.

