10.5 Analysis of Endpoints

Intent-to-Treat Population (ITT): The ITT population will include all subjects who are enrolled in the study. The ITT population will be the primary population for evaluating efficacy and subject characteristics.

As-Treated Population (AT): The AT population will include all subjects who receive at least 1 dose of study drug. The AT population will be the primary population for evaluating safety.

Analysis of Primary Endpoint

- Safety of repeated CED of MTX110 following standard of care focal radiotherapy will be assessed by monitoring for adverse events, scheduled laboratory assessments, vital sign measurements, and physical examinations for subjects who receive the drug. The severity of toxicities will be graded according to the NCI CTCAE v4.0. Adverse events and clinically significant laboratory abnormalities (meeting Grade 3, 4, or 5 criteria according to CTCAE) will be summarized by maximum intensity and relationship to study drug(s). Grade 1 and 2 adverse events will be summarized if related to study therapy. Descriptive statistics will be utilized to display the data on toxicity.

Analysis of Secondary Endpoint

- We will assess the preliminary efficacy using overall survival at 12 months (OS12) in 19 evaluable DIPG patients treated within the expansion cohort which will include subjects treated as part of the dose escalation portion of the trial on the recommended phase 2 dose (RP2D). Analyses will be performed after all enrolled subjects have completed 12 months, or whenever the status of all subjects has been established, whichever comes first. The primary analysis will be based on the Kaplan-Meier method. Kaplan-Meier estimates and the associated 95% CIs will be calculated for OS12. As described above, if 12 or more of the 19 patients are alive at 12 months, the null hypothesis that OS12 is 40% will be rejected.

Analysis of Exploratory endpoint

The exploratory aims associated with this study will be descriptive and will be limited to frequency tables and summary statistics.

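### If the first level that triggers the 3+3 fails, the level below becomes the RP2D with no further subjects required there, and the expansion has no numerical DLT boundary

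*Combined protocol and SAP*

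**What the plan says.** Section 10.2 starts with accelerated titration: "Each cohort will consist of one subject". Little is needed to move up: "A 14-day window of evaluation for toxicities is required for at least one subject at each dose level before determining the dose for the next" group. The switch to a 3+3 comes "At the second occurrence of any grade 2 toxicity during the first treatment cycle, or the first DLT occurrence during the first treatment cycle". At that point "two additional subjects will be accrued at the dose level that triggered the transition". The level fails with 2 or 3 DLTs in three subjects, or with more than 1 in six. In the six-subject case the text reads "more than one DLT and then the next lower dose level is the RP2D", and the three-subject case also names the next lower level. Section 5.5 repeats the rule. Neither section asks for more subjects at the lower level first.

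On progress, Section 2.3 reports "completed monitoring and DSMC approval of the first 4 dose levels as per the ATD", with no DLTs. Table 13 lists one evaluable patient at level 4.

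Section 10.5 assesses 12-month survival in 19 evaluable patients and counts escalation subjects treated at the RP2D among them. The first stopping rule in Section 10.3 is "The occurrence of 1 or more irreversible neurological deficits that are grade 3 or higher and definitely related to the procedure", with supporting MRI evidence. The other two concern irreversible deterioration while the infusion runs and failure to infuse because of surgical complications, each in more than 20% of subjects.

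**The concern.** Safety is the primary endpoint. A rejected level is judged on three to six children, while the level chosen in its place may rest on one child without a DLT. Up to 18 more children could then be treated there.

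Section 5.3 defines a DLT broadly. It includes intolerable grade 2 or any grade 3 or higher neurological toxicity attributed to the procedure or infusate, and related systemic toxicity of grade 3 or higher, whether or not it resolves. These events decide the RP2D in phase I. Once the expansion opens, no count of them triggers a study-wide decision. A poor choice of level could therefore persist until someone acts on general safety review.

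**Working it through.** **The plan's own figure.** The only operating characteristics stated are for 12-month survival. With N = 19 and rejection at 12 or more alive, P(X ≥ 12 | 40%) = 0.0352 and P(X ≥ 12 | 70%) = 0.818. This reproduces the stated 3.5%, and the power is close to the stated 80%. The plan states no operating characteristic for the dose rule.

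**Where the problem arises, by first triggering level**
- Levels 1 to 4: already cleared at the October 2018 cut-off.
- Level 5: level 4 becomes the RP2D under 10.2 and 5.5, and nothing in the text offsets this.
- Levels 6 and 7: Section 5.2 says intermediate level 5a or 6a will be tested, with no cohort size or decision rule. Sections 5.5 and 10.2 name the next lower level in Table 5.2.1 as the RP2D. These passages must be reconciled.
- The 3+3 passes its first level and fails at a later one: the level below already has three or six subjects, so the problem does not arise.

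**How likely the level 5 path is.** Let q be the true DLT rate at level 5. If a DLT is the trigger, the level survives only if all five added children are clear (two, then three). So P(trigger by DLT and fail) = q × [1 − (1 − q)^5]:
- q = 20%: 0.20 × 0.672 = 13%
- q = 35%: 0.35 × 0.884 = 31%
- q = 40%: 0.40 × 0.922 = 37%

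This leaves out the grade 2 trigger.

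**How little one child shows.** Let p be the true DLT rate at the level named RP2D (assumed). P(first child clear) = 1 − p. Given that, at most 1 DLT in 6 means at most 1 in the next five: (1 − p)^5 + 5p(1 − p)^4. Expected DLTs in the other 18 of the 19 are 18p, counting one 14-day window per child.

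| True rate p | First child clear | At most 1 in next 5 | Expected DLTs in 18 |
|---|---|---|---|
| 20% | 80% | 74% | 3.6 |
| 35% | 65% | 43% | 6.3 |
| 40% | 60% | 34% | 7.2 |
| 50% | 50% | 19% | 9.0 |

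For example, at 40%: 0.6^5 + 5 × 0.4 × 0.6^4 = 0.078 + 0.259 = 0.337.

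**Upper bounds on the DLT rate (exact, one-sided 95%).** After 0/1: 1 − 0.05 = 95%. After 0/6: 1 − 0.05^(1/6) = 39%. After 1/6: 58%.

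**Cost of a six-subject check at an acceptable level.** At p = 20%, a clear first child is followed by more than 1 DLT in the next five with probability 1 − 0.737 = 26%.

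**The case against.** A reader might infer that nothing would react to DLTs in the expansion. The documents do not support that. A DLT lowers that child's own dose (5.5, 10.2). Section 10.3 requires a safety and efficacy review with the FDA and DSMC before the efficacy study. Appendix E provides monthly monitoring through the DLT period, notice of unexpected DLTs to all sites within one business day, DSMC discussion of SAEs every six weeks, and DSMC notice if grade 3 to 5 event rates rise. What is missing is a numerical DLT-rate boundary. The pre-expansion review has no stated criterion and cannot supply observations that were never made.

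A reader might also infer that the RP2D will rest on one child. One is the minimum. Intra-patient escalation may expose more children to a level, although the rule neither requires nor counts those exposures. Table 13 is a snapshot, and the number enrolled is redacted. The design diagrams are not shown, so a confirmation step there cannot be excluded. Section 10.3 also allows added subjects for de-escalation or further dose exploration. Its minimum of five subjects in the 3+3 does not fit the path with 2 or 3 DLTs in three, which adds only two. That may hint at further subjects lower down, but no passage places them there.

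Nor would the finished trial lack safety data at the RP2D: Section 10.5 summarises toxicity in all treated subjects. The gap lies early in the expansion.

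Finally, at most 1 in 6 is stricter than the whole 3+3, which also passes 0 of 3. For a level not yet tested, at p = 40%, the full 3+3 passes with probability 0.6^3 + 3 × 0.4 × 0.6^2 × 0.6^3 = 31%. The six-subject check passes with probability 23%. This stands as a limit on calling the check simply the plan's own rule: it is the plan's six-subject branch.

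**Conclusion.** The concern holds on a defined path: the first level to trigger the 3+3 fails, and the level below has been cleared only under accelerated titration. At the reported cut-off that means level 5 triggering and failing. Levels 6 and 7 stay unresolved until Section 5.2 is reconciled with 5.5 and 10.2.

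On that path, a level with a true DLT rate of 40% has a 60% chance of a clear single child. Having shown one, it would meet a six-subject check only 34% of the time, and about 7 DLTs would be expected in the 18 further children. All DLT rates here are assumptions, since the documents give neither an observed nor a target rate. The calculations treat children as independent.

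This should be fixed. Because the path is conditional, an FDA/DSMC review precedes the expansion and other general safeguards apply, it is not an error that invalidates the design.

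**What to change.** In Sections 10.2, 5.5 and 10.3, state that the RP2D is provisional until six subjects have been observed at that level for the 14-day window with at most 1 DLT. The first expansion subjects supply the missing observations. If the criterion is not met, the DSMC reviews before further enrolment; the wording need not prescribe a dose. Say whether later-cycle exposures from intra-patient escalation count towards the six. Reconcile Section 5.2 on levels 5a and 6a with 5.5 and 10.2, including how many subjects are tested there and how the result is judged.

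The cost is protocol wording and short 14-day holds early in the expansion. The toxicity data are already collected after each infusion. Section 10.5 already counts subjects treated at the RP2D among the 19, so no patient is added if the level is confirmed. If the RP2D changes, children treated at the abandoned level may no longer count towards the 19. The main statistical downside is unneeded review: about 26% at a true rate of 20% after a clear first child.

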10.3 Sample Size and Accrual

The number of subjects enrolled in the safety study will depend upon the DLTs observed and the number of dose levels tested as the study progresses in accordance with an ATD followed by a 3+3 design. The ATD is expected to enroll 1 to 7 subjects with a minimum of 5 subjects in the 3+3 design. Additional subjects may be enrolled depending on the dose de-escalations, expansion of dose exploration, or exploration of intermediate doses that occur. Once these dose levels have been assessed, a detailed review of the safety and efficacy data will be performed and discussed with the FDA and the DSMC to discuss either further dose escalation or enrollment into the efficacy study.

Secondary Objective: The most recent Children’s Oncology Group study that treated children newly diagnosed with DIPG with a combination of radiation therapy and temozolomide resulted in an OS12 rate of 40% (SD ± 6.5%). A sample size of 19 patients achieves 80% power to detect a difference of 30% using a one sided exact binominal test. The target significance level is 5% and the actual significance level is 3.5% with this test. If 12 or more patients are alive at 12 months, the null hypothesis that OS12 is 40% will be rejected.

Stopping Rules:

Both the ATD and 3+3 have inherent stopping rules; however, it should be noted that this study will be stopped for further review by the DSMC and study team as well as FDA by:

- The occurrence of 1 or more irreversible neurological deficits that are grade 3 or higher and definitely related to the procedure based on evidence on MRI such as intraparenchymal hemorrhage, worsening edema or necrosis.

- If more than 20% of subjects develop significant, irreversible deterioration during the infusion.
- If more than 20% of subjects do not get study drug infused due to surgical complications during the catheter placement.

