6. TREATMENT PLAN

Subjects with a radiographic diagnosis of DIPG are potentially eligible for this protocol. Eligibility requirements and treatment begin after the completion of standard of care radiotherapy. Each subject will sign a consent form and complete eligibility procedures prior to enrollment, and baseline procedures prior to any study procedure. Treatment consists of intratumoral treatment of MTX110 by CED. The intent is to treat every 4-8 weeks with CED infusions for up to 24 months or until tumor progression or intolerable toxicity. If subjects continue to derive clinical benefit, discussion with investigators and study sponsor will determine feasibility and clinical appropriateness to continue therapy. Treatment consists of placement of up to 2 CED catheters into the tumor. The placement of catheters at the time of surgery is planned based on an MRI obtained prior to the procedure, using a predictive

placement algorithm. The infusions are done under direct MR guidance, using co-infused gadoteridol, to assess leakage and tumor volume coverage. Toxicity is assessed during and after each CED infusion, with the protocol defined dose limiting toxicity period being 14 days after each CED procedure. Subjects may be treated at the time of progression after discussion with the Study Chair(s) and Neurosurgical Chair(s), if the progression occurs outside of the previously treated area, and if the treating physician feels the subject is experiencing clinical benefit. Baseline and on-study laboratory studies, and every 4-8 week MRIs are done to assess toxicity and tumor status, as described in the study calendar, for up to 24 months or until progression or intolerable toxicity. After completing all study treatment, final assessments will be performed, including a 30-day toxicity check. All subjects are followed for toxicity, progression-free survival and overall survival.

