If a death occurs during the treatment phase of the study, or within 30 days after the last administration of the study drug(s), and is determined to be related either to the investigational drug or to any research related procedure, the Study Chair and the PNOC Operations Office must be notified by the member institution **within 1 business day**. The Study Chair or the PNOC Operations Office must then notify the UCSF DSMC Chair, or qualified alternate, within 1 business day of this notification. The contact may be by phone or e-mail. Each participating site will follow their institutional reporting guidelines to institutional DSMC.

7.4.3 **PNOC Reporting to UCSF Institutional Review Board (IRB)**

The PNOC Operations Office must report events meeting the UCSF IRB definition of “Unanticipated Problem” (UP) **within 10 business days** of awareness of the event.

Each participating site will follow their institutional reporting guidelines to the IRB.

7.4.4 **PNOC Reporting to the Food and Drug Administration (FDA)**

If the study is being conducted under an IND, the PNOC Operations Office is responsible for determining whether or not the suspected adverse reaction meets the criteria for expedited reporting in accordance with Federal Regulations (21 CFR §312.32).

The PNOC Operations Office must report in an IND safety report any suspected adverse reaction that is both serious and unexpected. The Sponsor-Investigator (PNOC) needs to ensure that the event meets all three definitions:

- Suspected adverse reaction
- Unexpected
- Serious

If the adverse event does not meet all three of the definitions, it should not be submitted as an expedited IND safety report.

The timeline for submitting an IND safety report to FDA is no later than **15 calendar days** after the PNOC Operations Office determines that the suspected adverse reaction qualifies for reporting (21 CFR 312.32(c)(1)).

Any unexpected fatal or life-threatening suspected adverse reaction will be reported to FDA no later than **7 calendar days** after PNOC initial receipt of the information (21 CFR 312.32(c)(2)).

Any relevant additional information that pertains to a previously submitted IND safety report will be submitted to FDA as a Follow-up IND Safety Report without delay, as

soon as the information is available (21 CFR 312.32(d)(2)).

7.4.5 **PNOC Reporting to Midatech Pharma (supplier of MTX110 injection)**

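### One irreversible grade 3 neurological deficit tied to the procedure stops the study, but no visible rule requires a hold for a related death outside that definition

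*Combined protocol and SAP*

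**What the plan says.** Section 10.3 notes that the accelerated and 3+3 stages have their own stopping rules. It then adds that "this study will be stopped for further review by the DSMC and study team as well as FDA by" any of three triggers:

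- Rule 1: "The occurrence of 1 or more irreversible neurological deficits that are grade 3 or higher and definitely related to the procedure", judged on MRI findings such as bleeding, oedema or necrosis.
- Rule 2: "If more than 20% of subjects develop significant, irreversible deterioration during the infusion".
- Rule 3: more than 20% of subjects left uninfused because of surgical complications at catheter placement.

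None of the three names death.

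A related death can be a DLT under 5.3, which covers grade 3 and above within 14 days. Section 6 describes the window as running after every infusion procedure, "with the protocol defined dose limiting toxicity period being 14 days after each CED procedure". In the accelerated stage, 10.2 moves to 3+3 on the second grade 2 toxicity in the first cycle or on "the first DLT occurrence during the first treatment cycle". After that switch, "two additional subjects will be accrued at the dose level that triggered the transition". One DLT in three adds three more subjects, and with six subjects the rule is "only one DLT and then dose escalation can occur based on Table 5.2.1".

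Sections 7.4.2 and Appendix E deal with a death on treatment, or within 30 days of the last dose, that "is determined to be related either to the investigational drug or to any research related procedure". They require notice to the study chair and operations office within one business day, and to the DSMC chair within one further business day. Appendix E also says whom to tell if enrolment is halted for safety. It does not say when enrolment must be halted.

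**The concern.** Safety is the primary endpoint, and each cycle is repeat catheter surgery in the brainstem of a child. The sponsor has already decided that one severe, permanent neurological injury from the procedure should stop the study without waiting for anyone to choose. A related death is worse, yet unless it fits rule 1 the plan leaves the pause to the judgement of those who are notified. The stated rules therefore rank one kind of grade 3 event above some grade 5 events. What is at stake is whether another child can be enrolled or escalated before a related death has been reviewed.

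**Working it through.** The point turns on text, so the check is to run each kind of related death through the stated rules.

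| Related death | Rule 1 | Cohort rules | Mandatory hold in visible text? |
|---|---|---|---|
| Procedural bleed, oedema or necrosis on MRI, rated definite | Plausibly met | DLT if within 14 days | Yes, by rule 1 |
| Same, rated only probable or possible | Not met | DLT if within 14 days and judged attributable | No |
| Neurological, attributed to the drug | Not met | DLT if within 14 days | No |
| Systemic | Not met | DLT if within 14 days | No |
| Outside rule 1, after day 14 | Not met | Not a DLT | No |
| Outside rule 1, after cycle 1, accelerated stage | Not met | Does not trigger the switch to 3+3 | No |
| Outside rule 1, expansion cohort | Not met | No DLT-count rule stated | No |

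**Rules 2 and 3.** Both need more than 20% of subjects. One case in 4 is 25% and qualifies; one in 5 is exactly 20% and does not. At 19 subjects it takes 4 cases (4/19 = 21.1%; 3/19 = 15.8%). At 26 it takes 6 (6/26 = 23.1%; 5/26 = 19.2%). A single death can meet them only among the first four subjects, and only if it arises during infusion or prevents infusion.

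**A fatal DLT in cycle 1.** The text of 10.2 handles grade 5 as it handles grade 3. The design switches to 3+3, two more children enter at that level, then three more if neither has a DLT. One DLT in six then allows escalation. Section 2.3 reports levels 1 to 4 cleared without a DLT, so among planned levels this now concerns 5 to 7.

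**Cost of a death-triggered pause.** The documents do not give the rate of disease deaths soon after an infusion, so this is a range on assumptions.

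- Inputs: median survival 9 months (Abstract); at least 26 subjects (3.2); a 30-day window, or 8 weeks as the longest planned treatment interval.
- Formula: proportion dying within t days = 1 − exp(−(ln 2 / median in months) × t / 30.44), assuming a constant hazard.
- Median 9 months: hazard 0.0770 per month. This gives 7.3% in 30 days and 13.2% in 8 weeks, or 1.9 to 3.4 of 26 children.
- Median 3 months from the last infusion (assumed, because treatment generally stops at progression and section 2.3 puts survival after that at months): hazard 0.2310. This gives 20.4% and 34.6%, or 5.3 to 9.0 of 26.
- If 10% to 50% of these deaths were rated at least possibly related (assumed): 0.2 to 1.7 pauses over the trial on the first median, 0.5 to 4.5 on the second.

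A trigger at probably or definitely related would produce fewer pauses than these. The documents do not show how many fewer.

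**The case against.** The best reply is that the safeguards already do the work.

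- Under 7.4 and Appendix E every serious adverse event, which includes any death, reaches the operations office within one business day whatever its attribution. The DSMC reviews such events on an ongoing basis.
- The FDA receives unexpected fatal suspected reactions within 7 calendar days (7.4.4).
- Section 3.2 calls for review with the FDA and DSMC once each dose level is assessed, and 2.3 confirms that the DSMC approved the first four levels.
- The study chair or co-chair signs off eligibility, and the operations office confirms dose assignments.
- Rule 1 plausibly catches the most obvious fatal risks of the procedure, and the only related event reported in 2.3 is grade 1 fatigue.
- Rule 1 itself needs judgements, on irreversibility and on relatedness.

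Most of this stands, and it limits the point. A reader might infer that the plan would let enrolment run on after a treatment-related death, or that a later-cycle death in the accelerated stage would meet no check. The documents do not support either reading: the reporting duties and the committee's dose-level approvals make a pause likely. A reader might also use the 3+3 probabilities of further accrual or escalation to size the risk. Those would be the same for any first DLT and assume that nobody intervenes, so they do not measure this gap.

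What remains is that these are duties to report, review and approve. Once the judgements under rule 1 are made, the stop is compulsory. Once a related death outside rule 1 is recognised, no visible text compels one.

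**Conclusion.** The point holds as a gap in the stated rules and is worth a small amendment. It does not show that children would in fact be enrolled unreviewed after a related death. The difference is between a required pause and a likely one, for deaths that are systemic, attributed to the drug, or not rated definitely related. No probability of such a death is offered, because the documents give none. The conclusion rests on the visible text; the two escalation diagrams and the institutional monitoring plans could not be read and might add a rule.

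It may be tempting to conclude that every possibly related death should stop accrual. That goes too far here: relatedness is hard to exclude in this disease, and on the assumptions above such a trigger could cause up to about 4.5 pauses from deaths due to disease.

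**What to change.** Add a bullet to 10.3, applying to both phases: any death during treatment or within 30 days of the last infusion that is judged probably or definitely related to study drug or procedure pauses new enrolment and dose escalation, including within-patient escalation, until ad hoc review by the DSMC, study team and FDA. Possibly related deaths go to prompt DSMC review without an automatic pause. Infusions for children already on treatment are decided case by case.

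Add a sentence to 10.2, mirrored in 5.5, which repeats the same rules: any fatal DLT goes to this review before another subject is accrued at that level.

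The change uses the existing committee and adds little text. Its price is an occasional short pause for a death later judged due to disease, less often than with a possibly-related trigger. The review should be ad hoc. The DSMC meets every six weeks and the entry window runs from 4 to 14 weeks after radiotherapy, so waiting for a scheduled meeting could use up to 6 of the 10 weeks in which a child may start treatment.
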